2.5.4 Supportive analyses

2.5.4.1 Supplementary analysis

The following supplementary analysis to the primary analysis for NRS will be performed on the FAS population.

to quantify the treatment effect of the investigational drug compared to placebo, that would have been observed had all patients remained on their assigned treatment for 12 weeks. The handling of post randomization events will be same as for the primary analysis, except that missing data after discontinuation for any reason will be imputed using the MAR assumption.

The supplementary estimand corresponding to this supplementary analysis is described in detail in the Estimand Charter.

2.5.4.2 Sensitivity analysis

A sensitivity analysis will be performed on the mFAS population using the same ANCOVA model as for the primary analysis.

2.6 Analysis of the key secondary objective

2.6.1 Key secondary endpoint

The key secondary efficacy variable will be the change from baseline to Week 12 in the Neurophathic Pain Symptom Inventory (NPSI) total score which is calculated as the sum of 10 descriptors outcome measure out of the 12 items measured in the NPSI.

The key secondary endpoint will be evaluated for the FAS.

2.6.2 Statistical hypothesis, model and method of analysis

To compare the efficacy of EMA401 over placebo in the NPSI total score the null hypothesis of superiority of EMA401 over placebo will be tested. The definitions of the estimands for the key secondary variable NPSI will also be detailed in an Estimand Charter.

The estimation of the treatment difference and missing data handling will be performed using the method of analyses mentioned for the primary analysis for NRS. Post randomization events will be handled in the same way as in the primary analysis for NRS.

The key secondary objective will be achieved if the EMA401 100 mg b.i.d. dose is statistically significant versus placebo in terms of NPSI total score after multiplicity adjustment. To preserve the family-wise error rate at the 2.5% level when comparing the EMA401 100 mg b.i.d. dose versus placebo on the two endpoints NRS and NPSI, statistical testing will be carried out using the graphical testing procedure as explained in Section 2.5.2.

The same ANCOVA model will be applied at the visits prior to Week 12. Multiplicity adjustment at visits prior to Week 12 will not be carried out.

The same supplementary analysis as for the primary endpoint will be performed.

Summary statistics by treatment and visit will be provided for the key secondary endpoint.

2.7 Analysis of secondary efficacy objective(s)

The following secondary efficacy variables will be evaluated for the FAS:

2.7.1 Responder Analysis

Responder analyses (based on at least a 30%, 50% improvement from baseline on NRS) will be performed in order to facilitate the interpretation of the results of the primary and supplementary analysis from a clinical relevance perspective. These analyses will be performed on the FAS population. One secondary estimand is considered, together with one supplementary estimand.

The secondary estimand and the supplementary estimand to the secondary estimand differ from the primary and supplementary estimand in two ways:

- First, the variable of interest is the responder status in NRS score, with response status corresponding to at least a 30% (50%) improvement in pain from baseline.
- Second, the measure of intervention effect is the odds ratio of the proportions of responders between investigational drug and placebo.

The other features characterizing these responder analyses are exactly the same as for the primary and the t supplementary analysis, respectively.

From an analysis point of view, the responder status for each patient will be calculated on the continuous weekly score measurements after missing data are multiply imputed based on the approach specified corresponding to the primary analysis and the supplementary analyses. If the patient is a completer but week 12 measurement is affected by the changes in doses of concomitant medication for PDN or the use of prohibited medication then the responder criteria will be defined based on the multiply imputed values by MAR. The resulting responder variable will be analyzed using a logistic regression model including all randomized patients and adjusting for the same covariates as the ANCOVA model for the primary analysis.

From an analysis point of view, the resulting responder variables will be analyzed using a logistic regression model including all randomized patients (FAS population) and adjusting for the same covariates as the ANCOVA model for the primary analysis. Odds ratios will be estimated along with their 95% CIs.

The responder analyses will be performed for each visit, with the obvious modification in the definition for the week of interest.

2.7.2 Other secondary efficacy objectives

1. BPI-SF interference total score will be summarized descriptively by treatment and visit.
2. Weekly mean of the 24-hour **worst** NRS pain score, using an 11-point Numeric Rating Scale (NRS). This variable will be summarized descriptively by treatment and visit.

3. Number of patients in each level of PGIC at end of study treatment will be presented by treatment. PGIC classification will also be combined into two categories: Either a "very much improved" or a "much improved" reported, and the five remaining categories.
4. Insomnia Severity Index (ISI) will be summarized descriptively by treatment and visit.
5. The proportion of patients who need rescue medication (at each visit and at least once during the study) will be evaluated separately for the double-blind Treatment epoch and Treatment withdrawal epoch.
6. The Kaplan-Meier estimates of the proportion of patients with rescue medication intake during the double-blind Treatment epoch, along with the associated 95% confidence intervals using the Greenwood's formula will be provided.

2.8 Safety analyses

Safety analyses will be conducted using the safety (SAF) population. Patients will be analysed by the actual treatment they received. All the safety analyses including AEs, vital signs, laboratory parameters, ECGs [REDACTED] will be reported for double-blind treatment period as well as for the treatment withdrawal period separately.

2.8.1 Adverse events (AEs)

Treatment-emergent adverse events (TEAEs) are defined as any adverse events that develops after initiation of study treatment until the end of study visit or any event already present that worsens following exposure to the study treatment.

If an adverse event starts at the date of week 12 visit it should be allocated to the treatment epoch and not to the treatment withdrawal epoch. Adverse events reported 21 days after end of study date in the scope of USM will not be included in the summary tables, but will be listed.

TEAEs will be summarized (number of cases as a percentage of number at risk) by treatment group separately for Treatment epoch and Treatment withdrawal epoch. Number and percentage of patients with TEAE will be summarized by primary system organ class and preferred term for each treatment group during the double-blind Treatment epoch and during the double-blind Treatment withdrawal epoch. Severity will be classified as "mild", "moderate" and "severe". Serious TEAEs, TEAEs by maximum severity and TEAEs leading to premature discontinuation from study drug will be presented in a similar format as adverse events. Additionally, a listing of patients with TEAE will be presented. Drug abuse-related adverse events (identified using a pre-specified search criterion) will be summarized during the double-blind Treatment epoch. To assess the potential for withdrawal effect, drug abuse-related adverse events will be summarized for the double-blind Treatment withdrawal epoch.

The following additional analysis will be performed.

- Analysis of treatment-emergent adverse events with onset date before 25-Feb-2019

For rash adverse events, following details will be listed:

- Laterality and location of rash

- Did the subject start any new topical non-pharmaceutical products within the last 14 days prior to the start of rash?
- Topical Non-pharmaceutical Products related to the event of rash including soap, detergent, perfume, cologne and lotion.
- Were there any additional contributing factors that may have led to the rash?
- Did the dermatologist agree with the event?
- Additional investigation performed to diagnose that event: yes, no

For the legal requirements of ClinicalTrials.gov and EudraCT, two required tables on <on-treatment/treatment emergent> adverse events which are not serious adverse events with an incidence greater than X% and on <on-treatment/treatment emergent> serious adverse events and SAE suspected to be related to study treatment will be provided by system organ class and preferred term on the safety set population.

If for a same patient, several consecutive AEs (irrespective of study treatment causality, seriousness and severity) occurred with the same SOC and PT:

- a single occurrence will be counted if there is ≤ 1 day gap between the end date of the preceding AE and the start date of the consecutive AE
- more than one occurrence will be counted otherwise.

For occurrence, the presence of at least one SAE / SAE suspected to be related to study treatment / non SAE has to be checked in a block e.g., among AE's in a ≤ 1 day gap block, if at least one SAE is occurring, then one occurrence is calculated for that SAE.

The number of deaths resulting from SAEs suspected to be related to study treatment and SAEs irrespective of study treatment relationship will be provided by SOC and PT.

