3.1 Study design

The study is interventional, randomized, parallel, placebo-controlled, double-blind treatment.

[figure not shown]
The study will consist of a Screening epoch (up to 4 weeks), a double-blind Treatment epoch (12 weeks), and a double-blind Treatment withdrawal epoch (1 week). Concomitant use of pregabalin or duloxetine at stable doses is allowed (Section 5.5.7). Based on historical data study will enroll approximately 50% of patients on concomitant pregabalin or duloxetine.

- Patients will be randomized in a 1:1 ratio to treatment with placebo or EMA401 100 mg b.i.d.

Overall approximately 400 patients will be enrolled in the study (i.e. approximately 200 patients will be enrolled in each treatment arm). End of Trial (EoT) will occur when the last patient completes last visit (LPLV).

Figure 3-1 presents an overview of the study design.

Figure 3-1 Study design

Screening epoch (Up to 4 weeks)

Potential participants will be required to provide written informed consent prior to any study-specific Screening procedures being performed. Once informed consent is obtained,

patients will be evaluated for eligibility based on the inclusion and exclusion criteria (see [Section 4](#)), which will require review of medical history and concomitant medications, vital signs, physical examination, assessment of patients' current pain scores using the NRS, 12-lead electrocardiogram (ECG), and clinical laboratory evaluations.

During Screening, site staff must ensure that the patient is not taking any prohibited concomitant medications or combination therapy for neuropathic pain treatment. Patients who pass preliminary Screening assessments will receive their electronic patient reported outcome (ePRO) diary (eDiary) device. Patients completing their 7 day baseline 24-hour pain intensity scores will return to the study site at Visit 101 (i.e. Baseline).

The patient's final eligibility will be based on an assessment of their average pain intensity scores using a proprietary screening algorithm ([Appendix 4](#)) prior to randomization.

General principles of the algorithm include:

Exclusion of patients with scores below the minimum mean baseline pain intensity of "4" using the NRS scale; and patients who:

- Were not compliant in completing the required data

OR

- Did not record accurate pain scores

OR

- Who had unacceptable variability in their baseline intensity.

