Site staff will need to check the electronic tablet to see if the patient meets these criteria to continue in the study and document the outcome in the patient's source document.

Treatment epoch (12 weeks)

Patients completing all Screening assessments will then be randomized into a 12-week double-blind Treatment epoch at the Baseline visit (V101). Patients will visit the study site for assessments that are outlined in the visit assessment schedule ([Table 6-1](#)). At each scheduled visit Investigators/site staff will perform various assessments outlined in the visit assessment schedule and will review the patient's weekly pain eDiary scores from the prior week(s) for compliance and entry errors, retraining the patient on eDiary entry as needed. Patients will be required to bring their eDiary device to every site visit. Patients will be instructed to continue recording their 24-hour average and worst pain intensity scores each day for the remainder of the study. Patients will be required to bring their previously dispensed supply of study medication to each scheduled visit in order that site staff can assess patient's compliance with the dosing regimen. Patients should bring their duloxetine (if applicable) with them to the study visits where PK is collected so it may be administered after the PK assessment, as required.

Treatment withdrawal epoch (1 week)

For patients who complete the 12 week Treatment Epoch, there will be a 1-week, double-blind Treatment withdrawal epoch. Patients receiving placebo treatment during the 12-week double-blind Treatment epoch will remain on placebo during the double-blind Treatment withdrawal epoch. Patients receiving active treatment will be randomized in a 1:1 ratio to

either stop treatment (i.e. receive placebo) or to continue the active treatment assigned during the double-blind Treatment epoch.

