- Abnormal hematology evaluation, defined as any of the following, requires temporary discontinuation of study medication and repeat testing within 48 hours (via central or local laboratory) and follow-up until recovery to \leq grade 1 Common Terminology Criteria for Adverse Events (CTCAE). Study treatment must be permanently discontinued thereafter if hematology values are abnormal again (as defined below) after re-initiation of study treatment.
 - Platelets $<50 \times 10^9/L$
 - Absolute neutrophil count $<1.0 \times 10^9/L$
 - Hemoglobin $<80 \text{ g/L}$

If discontinuation of study treatment occurs, the patient should NOT be considered withdrawn from the study. The patient should return to the clinic as soon as possible, after discontinuation of study drug, for a study treatment discontinuation visit as detailed in [Table 6-1](#). The investigator must determine the primary reason for the patient's premature discontinuation of study treatment and record this information in the on the Dosage Administration eCRF.

Patients who discontinue study drug should be treated according to the best standard of care and be encouraged to stay in the study and continue to be followed with an abbreviated schedule of assessments as indicated in [Table 6-2](#).

If the patient cannot or is unwilling to attend any visit(s), the site staff should maintain regular telephone contact with the patient, or with a person pre-designated by the patient. This telephone contact should preferably be done according to the abbreviated study visit schedule.

The investigator must also contact the IRT to register the patient's discontinuation from study treatment.

If study drug discontinuation occurs because treatment code has been broken, please refer to [Section 5.5.9](#).

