5.6.5 Early study termination by the sponsor

The study can be terminated by Novartis at any time for any reason. This may include reasons related to the benefit risk assessment of participating in the study, practical reasons, or for regulatory or medical reasons (including slow enrolment). Should this be necessary, the patient must be seen as soon as possible and treated as a prematurely discontinued patient. The investigator may be informed of additional procedures to be followed in order to ensure that adequate consideration is given to the protection of the patient's interests. The investigator will be responsible for informing the Institutional Review Board/Independent Ethics Committee (IRBs/IECs) of the early termination of the trial.

6 Visit schedule and assessments

[Table 6-1](#) lists all of the assessments and indicates with an "X" or "S" when the visits are performed.

[figure not shown]
Patients must be seen for all visits on the designated day, or as close to it as possible. Missed or rescheduled visits should not lead to automatic discontinuation. Patients who prematurely discontinue the study treatment for any reason should be scheduled for a visit as soon as

possible, at which time all of the assessments listed for the Treatment Discontinuation visit (TD) will be performed. At this visit, all dispensed investigational product should be reconciled and the adverse event and concomitant medications reconciled on the CRF. If patients then agree to continue in the study (for further safety and efficacy data collection), subsequent visits will then be according to the Abbreviated schedule of assessments for patients with study treatment discontinuation as outlined in [Table 6-2](#). Patients following the Abbreviated schedule of assessments must continue to adhere to the protocol requirements for changes to concomitant medications for neuropathic pain, rescue medication and prohibited medications.

Patients will be contacted for safety evaluations during the 30 days following the last administration of study treatment.

Table 6-1 Assessment schedule

Epoch	Screening	Treatment									Treatment withdrawal
		101	102	103	104	105	106	107	199	TD visit	
Visit	1	101	102	103	104	105	106	107	199		201
Week	-5 to -1	0 (BL)	1	2	4	6	8	10	12	TD visit	13
Day	-35 to -7	1	8	15	29	43	57	71	85		92
Informed consent	X										
Inclusion/Exclusion criteria	X										
Demography	X										
Disease & Medical History	X										

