7.1 Adverse events

An adverse event (AE) is any untoward medical occurrence (e.g., any unfavorable and unintended sign [including abnormal laboratory findings], symptom or disease) in a subject or clinical investigation subject *after providing written informed consent* for participation in the study until the end of study visit. Therefore, an AE may or may not be temporally or causally associated with the use of a medicinal (investigational) product.

In addition, all reports of intentional misuse and abuse of the product are also considered an adverse event irrespective if a clinical event has occurred.

The occurrence of adverse events must be sought by non-directive questioning of the patient at each visit during the study. Adverse events also may be detected when they are volunteered by the patient during or between visits or through physical examination findings, laboratory test findings, or other assessments.

Abnormal laboratory values or test results constitute adverse events only if they fulfill at least one of the following criteria:

- they induce clinical signs or symptoms,
- they are considered clinically significant,
- they require therapy.

Clinically significant abnormal laboratory values or test results must be identified through a review of values outside of normal ranges/clinically notable ranges, significant changes from baseline or the previous visit, or values which are considered to be non-typical in patient with underlying disease. Investigators have the responsibility for managing the safety of individual patient and identifying adverse events. Alert ranges for laboratory and other test abnormalities are included in [Appendix 1](#).

Adverse events must be recorded in the Adverse Events CRF under the signs, symptoms or diagnosis associated with them, accompanied by the following information:

- the severity grade
 - mild: usually transient in nature and generally not interfering with normal activities
 - moderate: sufficiently discomforting to interfere with normal activities
 - severe: prevents normal activities
- its relationship to the study treatment
 - Yes
 - No
- its duration (start and end dates) or if the event is ongoing an outcome of not recovered/not resolved must be reported.
- whether it constitutes a serious adverse event (SAE - See [Section 7.2](#) for definition of SAE) and which seriousness criteria have been met.
- action taken regarding investigational treatment

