7.2.2 SAE reporting

To ensure patient safety, every SAE, regardless of causality, occurring after the patient has provided informed consent and until 30 days after the last study visit must be reported to Novartis safety within 24 hours of learning of its occurrence. Any SAEs experienced after the 30 day period after the last study visit should only be reported to Novartis safety if the investigator suspects a causal relationship to study treatment.

All follow-up information for the SAE including information on complications, progression of the initial SAE and recurrent episodes must be reported as follow-up to the original episode within 24 hours of the investigator receiving the follow-up information. An SAE occurring at a different time interval or otherwise considered completely unrelated to a previously reported one must be reported separately as a new event.

Information about all SAEs is collected and recorded on the Serious Adverse Event Report Form; all applicable sections of the form must be completed in order to provide a clinically thorough report. The investigator must assess the relationship of each SAE to study treatment, complete the SAE Report Form in English, and submit the completed form within 24 hours to Novartis. Detailed instructions regarding the submission process and requirements for signature are to be found in the investigator folder provided to each site.

Follow-up information is submitted as instructed in the investigator folder. Each re-occurrence, complication, or progression of the original event must be reported as a follow-up to that event regardless of when it occurs. The follow-up information should describe whether the event has resolved or continues, if and how it was treated, whether the blind was broken or not, and whether the patient continued or withdrew from study participation.

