9.5.2.1 Adverse events

Treatment-emergent adverse events (TEAEs) are defined as any adverse events that develops after initiation of study treatment or any event already present that worsens following exposure to the study treatment.

TEAEs will be summarized (number of cases as a percentage of number at risk) by treatment group. Number and percentage of patients with TEAE will be summarized by primary system organ class and preferred term for each treatment group during the double blind Treatment epoch and during the double-blind Treatment withdrawal epoch. Relationship to study medication will be classified as related (“probably related” and “possibly related”) and unrelated (“not related”). Severity will be classified as “mild”, “moderate” and “severe”. Serious TEAEs, drug related TEAEs, TEAEs by maximum severity and TEAEs leading to premature discontinuation from study drug will be presented in a similar format as adverse events. Additionally, a listing of patients with TEAE will be presented. Drug abuse-related adverse events and suicidality will be summarized during the double-blind Treatment epoch and treatment withdrawal epoch. The search criterion for each of these events will be defined based on MedDRA. The drug abuse-related adverse events will be summarized for the double-blind Treatment withdrawal epoch to assess the potential for withdrawal effect.

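### The TEAE window closes at the end-of-study visit with no link to last dose, so SAEs reportable for 30 more days fall outside the serious-TEAE summary and off-drug time depends on disposition

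*SAP*

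**What the plan says.** - **SAP 2.8.1** defines a new-onset TEAE as "any adverse events that develops after initiation of study treatment until the end of study visit". The second limb, worsening of an event already present, has no end date.
- **Protocol 9.5.2.1** has "any adverse events that develops after initiation of study treatment or any event already present that worsens following exposure to the study treatment", with no end date for either limb. SAP Section 4 does not list the added end point as a change.
- **Protocol 7.1** collects AEs from consent "for participation in the study until the end of study visit". For non-serious events the SAP window therefore ends where collection ends.
- **Protocol 7.2.2** says that every SAE "until 30 days after the last study visit must be reported to Novartis safety".
- **Protocol Section 6** plans a further contact: "Patients will be contacted for safety evaluations during the 30 days following the last administration of study treatment".
- **Protocol 5.6.2** encourages patients who stop study drug to stay in the study and "continue to be followed with an abbreviated schedule of assessments as indicated in" Table 6-2, which runs to Week 12.
- **SAP 2.8.1, next paragraph**, keeps USM-related AEs reported 21 days after the end-of-study date out of the summary tables and lists them. SAP 2.8.3 has the same rule for laboratory data.
- **SAP 2.8.2** lists all deaths.

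**The concern.** Safety and tolerability, including SAEs, is a stated secondary objective. Three things are at stake.

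1. **Completeness.** The protocol obliges sites to report SAEs for 30 days after the last visit, but the window used for the serious-TEAE table has already closed. A reader of that table would not know that collected SAEs lie outside it.
2. **Consistency.** The definition and the 21-day USM sentence sit in the same section and imply different ends.
3. **Interpretation.** Because the window ends at a visit and not at a set time after last dose, the off-drug time it contains varies with how the patient left treatment. For one group it closes at the last dose. For another it can run for weeks with no study drug, and every new event in that time counts as treatment-emergent.

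**Working it through.** The plan states no figure on this point to reproduce. The check is date arithmetic on the visit schedule.

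**Inputs**
- Visit days from Protocol Table 6-1: Week 0 = Day 1, Week 1 = Day 8, Week 4 = Day 29, Week 8 = Day 57, Week 10 = Day 71, Week 12 (Visit 199) = Day 85, Week 13 (Visit 201) = Day 92. All fit day = 7 × week + 1.
- Table 6-1, footnote 7: the last treatment-epoch dose is taken on the morning of Visit 199.
- Protocol Table 5-1: placebo/placebo, EMA401/EMA401 and EMA401/placebo in the ratio 2:1:1.
- SAP, Amendment 1 text: 137 of 400 planned patients were randomized.

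**Off-drug days inside the TEAE window** = day of end-of-study visit − day of last EMA401 dose

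| Patient | Calculation | Days |
|---|---|---|
| EMA401 in both epochs, finishes | 92 − 92, or 92 − 91 | 0 to 1 |
| EMA401 then placebo, finishes | 92 − 85 | 7 |
| Stops at Week 10, followed to Week 12 | 85 − 71 | 14 |
| Stops at Week 4, followed to Week 12 | 85 − 29 | 56 |
| Stops at Week 1, followed to Week 12 | 85 − 8 | 77 |
| Stops on Day 1, followed to Week 12 | 85 − 1 | 84 |

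**Patients in the 0-to-1-day group.** One quarter of those randomized: 137 / 4 ≈ 34 assigned, if the realized split followed 2:1:1. Fewer reached Week 13, since the amendment refers to many discontinuations caused by termination. The originally planned 400 would have given 400 / 4 = 100.

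**SAE reporting end** = last study visit + 30
- Finisher: 92 + 30 = Day 122, against a TEAE window closing on Day 92.
- Early stopper followed to Week 12: 85 + 30 = Day 115, against Day 85.

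In both cases 30 days of required SAE reporting follow the close of the TEAE window.

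**Where a post-visit SAE would appear.** The serious-TEAE table excludes it by definition. The registry SAE table in SAP 2.8.1 leaves the choice between on-treatment and treatment-emergent open, so it may inherit the same limit. Deaths are listed, and late USM reports are listed. No table or listing is stated for any other post-visit SAE.

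**Effect of a window of last dose of study drug + 30 days**
- EMA401 in both epochs: 92 + 30 = Day 122 (Day 121 if the last dose was on Day 91).
- EMA401 then placebo: last dose of study drug includes placebo, so 7 + 30 = 37 days off EMA401.
- Stop at Week 1: 8 + 30 = Day 38. New events on Days 39 to 85 would be shown separately.
- Stop at Week 8: 57 + 30 = Day 87, beyond Day 85, so nothing is trimmed. Only stops before Day 85 − 30 = Day 55 are affected.

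**The case against.** **Nothing is lost.** A reader might infer that the plan discards SAEs. The documents do not support that. Post-visit SAEs still go to the sponsor's safety group, all deaths are listed, deaths resulting from SAEs are tabulated by system organ class and preferred term, and late USM events are listed. What stands is narrower: the serious-TEAE summary excludes these SAEs, and the SAP states no other place for most of them.

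**The 21-day sentence may not conflict.** It refers to when an event is reported, while the definition refers to when it develops. It could therefore cover late reports of earlier onsets. The SAP does not say so, and the natural implication is that some events after end of study enter the tables. The two still need reconciling.

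**Differing windows are a design choice.** Collecting SAEs for longer than non-serious AEs is a choice, not an error. For patients who stay on EMA401 to Week 13, the 30 days after last dose and the 30 days after last visit almost coincide. This is fair, but it does not explain why the analysis window stops short of the SAE collection window.

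**A visit-based window has its own logic.** The treatment-epoch table compares both arms over the same planned period to Day 85, whether or not drug was stopped. Cutting at last dose plus a lag makes observation time depend on discontinuation, which may itself differ by arm. This stands. It is why the last-dose window should be added and should not replace the planned table. It also means that a biased arm comparison, which a reader might infer, has not been shown.

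**Side effects of other treatment.** A reader might infer from the best-standard-of-care wording in Protocol 5.6.2 that side effects of new analgesics would be charged to the assigned arm. Section 6 and the footnotes to Table 6-2 require early stoppers to keep to the concomitant, rescue and prohibited medication rules, so that inference is not supported.

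**The 30-day lag has no pharmacological basis in the documents.** No half-life is given, and the contraception requirement runs only 3 days after stopping. The 30 days is borrowed from the protocol's own safety contact and is a convention.

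**Conclusion.** The point holds as a gap in the safety summaries and an inconsistency within SAP 2.8.1. Read literally, the definition leaves 30 days of reportable SAEs outside the serious-TEAE summary. Off-drug time within the window ranges from 0 to 1 day, through 7 days, to at most 84 days, depending on disposition. The long tails need an early stop followed by continued follow-up, and SAP 2.5.2 expects such data to be sparse.

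The figure of about 34 assumes that the randomized patients split 2:1:1, and it counts assignment, not completion. The documents give no numbers of early stoppers in follow-up or of post-visit SAEs, so the effect on the tables is unknown and may be small. The case for acting is that the change is cheap and makes the SAE summary complete.

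A reader might go further and ask for non-serious AE recording to be extended past the last visit. The SAP gives 25-Feb-2019 as the termination date and is itself dated 18-Jun-2019, so a change to Protocol 7.1 at that stage could not create data.

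**What to change.** In SAP 2.8.1, before database lock:

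1. **Serious events.** Include SAEs collected under Protocol 7.2.2, up to 30 days after the last study visit, in the serious-AE summary. State which epoch or table receives them, and reconcile this with the 21-day USM sentence by saying whether that cut works on onset or report date.
2. **On-drug view.** Add a by-arm TEAE table limited to onset from first dose to last dose of study drug + 30 days. Show later off-drug events in retrieved drop-outs separately. Keep the planned by-epoch table alongside it.

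Record the final definition in SAP Section 4, since it differs from Protocol 9.5.2.1.

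**Cost.** One date rule and one extra table, using data the protocol already requires. **Limits.** For finishers only SAEs will populate the added days, because Protocol 7.1 ends non-serious AE collection at the end-of-study visit. The added table does not fully equalize time off EMA401 (about 37 days for those switched to placebo, 30 for those who stayed on), so its footnote should say that last dose means last dose of study drug, placebo included.
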